Venous thromboembolism (VTE) is a common, potentially life-threatening complication in high-risk trauma patients. With emerging evidence demonstrating around 50% of trough serum anti-factor Xa (anti-Xa) concentrations are subtherapeutic and associated with increased VTE risk, the purpose of this pilot study is to evaluate the safety and efficacy of a novel enoxaparin dosing strategy based on anti-Xa values. High-risk patients (e.g., risk assessment profile score ≥ 5) initiated on enoxaparin 30 mg q12h per current trauma team standard of care. Patients will be excluded for renal dysfunction (Cockcroft-Gault calculated creatinine clearance < 30 mL/min or patients on continuous renal replacement therapy), weight < 50 kg or > 150 kg, nephrotic syndrome, platelet count $< 50 \times 10^3$, allergy to heparin, patients on or requiring therapeutic anticoagulation at or within 24 hours of admission, isolated intracranial hemorrhage, known hyperbilirubinemia, pregnancy, or incarceration. Primary outcome is the comparison of antithrombin-III (AT-III), proportion of anti-Xa goal achievement at first, second, and all assessments, and time to goal anti-Xa. Patient outcomes include VTE events, bleeding outcomes, patients with bioaccumulation, and risk factors for low anti-Xa.

Purpose of Study

The purpose of this pilot study is to compare two enoxaparin dosing strategies: BID dosing and a dosing strategy based on anti-Xa values in high-risk trauma patients. Specific aims include: 1) to compare the extent of reduced AT-III activity between patients with anti-Xa ≥ 0.1 IU/mL and < 0.1 IU/mL upon initial assay and determine the proportion of patients who reach goal anti-Xa and time to goal anti-Xa between two dosing strategies: enoxaparin 40 mg every 12 hours (with consideration to increase to 50 mg every 12 hours if recheck anti-Xa is not at goal; see section 6) and enoxaparin 30 mg every eight hours; 2) to compare anti-Xa adjusted enoxaparin-dosing strategies based on VTE, bleeding rates, transfusion requirements, drug discontinuation rate and bioaccumulation, and 3) to determine patient-specific factors that correlate to subtherapeutic anti-Xa such as serial AT-III activity, weight, body mass index, age, cumulative fluid administration and thromboelastography (TEG).

Background

Background and Significance

Robinson¹⁴ performed a prospective, randomized trial following serial anti-Xa levels at baseline, 4, 12, 16, and 24 hours for three days in medical/surgical ICU patients receiving enoxaparin 40 mg once daily versus 30 mg twice daily, 40 mg twice daily, or 1 mg/kg once daily. Majority of patients (88%) were admitted for medical, not surgical, diagnoses. An anti-Xa between 0.1 – 0.4 IU/mL was maintained for 33.3% in 40 mg daily group, 41.7% in 30 mg twice-daily group, 83% in 1 mg/kg daily group, and 91.7% in 40 mg twice-daily group of the study period. Mean steady-state peak anti-Xa levels were 0.13 IU/mL for 40 mg daily, 0.15 IU/mL for 30 mg twice daily, 0.33 IU/mL for 40 mg twice daily, and 0.40 IU/mL for 1 mg/kg daily. The authors concluded that enoxaparin 40 mg daily and 30 mg twice daily may provide insufficient VTE prophylaxis, but the ideal dose is still unknown.

Increased VTE rates have been seen in patients with subtherapeutic anti-Xa values. Malinoski¹⁵ found that of 54 patients on enoxaparin 30 mg every 12 hours, 27 (50%) had subtherapeutic anti-Xa troughs and a statistically significant higher DVT rate than those with appropriate levels (37% vs. 11%, $p = 0.026$). Mean peak anti-Xa values were also lower in the subtherapeutic group (0.17 ± 0.1 IU/mL vs. 0.27 ± 0.1 IU/mL, $p < 0.001$); however, peak anti-Xa values were not different in those with and without DVT (0.23 ± 0.12 IU/mL vs. 0.23 ± 0.1 IU/mL, $p = \text{NS}$). A subsequent enoxaparin anti-Xa dose-adjusted protocol targeting peak anti-Xa levels between 0.2 – 0.4 IU/mL showed 18 (29.5%) of 61 patients on 30 mg twice-daily enoxaparin were at goal anti-Xa after the third dose.¹⁶ Only 5 (8.2%) patients, all in the therapeutic peak anti-Xa group, had a trough anti-Xa > 0.1 IU/mL. VTE events occurred in three patients in the entire study cohort (4.9%). Of the 27 patients with dosage adjustments, 22 (81.5%) patients received enoxaparin 40 mg twice daily, four patients received 50 mg twice daily (14.8%), and 1 patient received 60 mg twice daily (3.7%). Of note, there were no major bleeding events, which is not surprising given the anti-Xa peak goal is much lower when compared to standard therapeutic dosing goals (e.g., 0.5 – 1.1 IU/mL). Finally, a before-and-after study evaluated an anti-Xa adjusted dalteparin dosing strategy in high-risk (risk assessment profile [RAP] ≥ 5) trauma patients.¹⁷ High-risk patients were initiated on dalteparin 5000 units daily with a 12-hour anti-Xa value drawn after the first dose in the post-protocol group. If the 12 hour anti-Xa was < 0.1 IU/mL, the dose was increased to 5000 units twice-daily. Low trough anti-Xa was seen in 51% of post-group patients. VTE was lower in the post-protocol group (7.0% vs. 12.8%, $p = 0.009$) and higher in the subgroup of patients with a subtherapeutic trough anti-Xa (14.4% vs. 5.4%, $p = 0.05$). Therefore, anti-Xa adjustment of LMWH may result in fewer VTE events. No difference in blood transfusion after the first 48 hours was noted, suggesting appropriate safety with an anti-Xa driven dosing protocol for dalteparin.

Previous studies have tried to identify predictors for low anti-Xa concentrations. Young age, high body weight, edema, and low peak anti-Xa concentration have been associated with low trough anti-Xa.^{11, 15, 17} AT-III concentrations have not been collected or evaluated in many previous studies. Low AT-III concentrations have not been evaluated as a risk factor for low anti-Xa. Theoretically, low serum AT-III may represent a reduction in substrate to which LMWH can bind and exert anticoagulant effects. Hence, LMWH effectiveness and anti-Xa may be reduced.

Pharmacokinetic / Safety Information

Previous pharmacokinetic studies evaluating enoxaparin prophylaxis and anti-Xa levels suggest high inter-patient variability, especially in critically ill patients (table 1).^{11-12,14} However, the mean maximum serum concentration (C_{max}) did not reach the lower threshold for therapeutic dosing. Therapeutic enoxaparin anti-Xa concentrations are between 0.5 – 1.1 IU/mL for 1 mg/kg every 12 hours, and 1.0 – 2.0 IU/mL for 1.5 mg/kg every 24 hours.¹⁹ No major bleeding events were identified in previous studies.^{12,14} Additionally, evaluation of anti-Xa adjusted dalteparin dosing found no difference in transfusion requirements.¹⁷ Other evaluations of enoxaparin have found few minor bleeding events such as hematoma following total hip arthroplasty, ecchymosis, hematuria, and epistaxis.^{10,20} Based on these previous pharmacokinetic evaluations, patients enrolled in the proposed study would achieve a steady state peak between 0.3 – 0.5 IU/mL and a steady state trough between 0.1 – 0.3 IU/mL. Maintenance of said anti-levels should prevent major bleeding events. Additionally, exclusion of patients with poor renal function, defined as a Cockcroft-Gault calculated creatinine clearance < 30 mL/min will reduce the risk of bleeding events due to reduced drug elimination.

Table 1. Previous pharmacokinetic analyses of enoxaparin.

Trauma Population	Cmax (IU/mL)	Trough (IU/mL)	Half-life (hours)	AUC ₀₋₁₂ (IU/L per hour)	Vd (mL/kg)
Non-Edematous* ¹¹ (30 q12h; n = 11)	0.27 (0.19-0.59)	-	1.67 (0.64-3.92)	1.57 (0.91-3.83)	45.8 (28.9-76.4)
Edematous* ¹¹ (30 q12h; n = 10)	0.12 (0.07-0.34)	-	0.68 (0.31-1.97)	0.63 (0.34-2.18)	43.9 (31.2-68.6)
Rutherford ¹² (40 mg q24h; n = 17)	0.195±0.088	0.044±0.043	-	-	-
Robinson ¹⁴ (40 mg q24h; n = 20)	0.13	-	-	-	-
Robinson ¹⁴ (30 mg q12h; n = 30)	0.15	-	-	-	-
Robinson ¹⁴ (40 mg q12h; n = 40)	0.33	-	-	-	-
Robinson ¹⁴ (1 mg/kg q24h; n = 19)	0.40	-	-	-	-

Study Justification

Ideal enoxaparin dose for VTE prevention in high-risk trauma patients is unknown. Predictors and explanations for low anti-Xa are also unknown. With emerging evidence demonstrating around 50% of trough anti-Xa concentrations are subtherapeutic and associated with increased VTE risk, the purpose of this study is to compare AT-III serum concentrations as a predictor of low anti-Xa. Secondly, the study will compare two enoxaparin dosing. Ultimately, this information can be used to develop an optimum protocol for patient-specific enoxaparin dosing for VTE prevention to improve patient outcomes.

METHODS**Study design**

This is an investigator-initiated, single-center, prospective, non-blinded, randomized controlled trial. Multi-system trauma patients between 18-80 years old admitted to the University of Cincinnati Medical Center (UCMC), an urban American College of Surgeons-verified Level 1 trauma center will be identified by the Trauma Surgery team. The trauma team will inform study personnel of these patients once enoxaparin is initiated. These patients will be screened for inclusion in the study. Patients who meet inclusion criteria will be administered informed consent by study personnel in their rooms. Patients in the surgical intensive care unit (SICU) and on the surgical floor are eligible for enrollment if all other inclusion and exclusion criteria are met. Informed consent will be obtained prior to enrollment. Goal enrollment is 200 patients with 100 patients in the control group and 50 patients in each randomization group.

Research data collection/study procedures

Patients will be screened daily by the trauma team. Research personnel will be alerted to potential patients for enrollment.

Intervention

Serum AT-III and anti-Xa will be drawn eight hours after the third dose of enoxaparin 30 mg q12h. Serum assays after at least the third dose should approximate drug steady state trough concentrations. Patients with a serum anti-Xa ≥ 0.1 IU/mL will remain on enoxaparin 30 mg every 12 hours and will be the control group. Patients with undetectable anti-Xa (intervention groups), defined as a trough anti-Xa < 0.1 IU/mL, will be randomized to receive either:

- a. Enoxaparin 40 mg every 12 hours (group 1)
- b. Enoxaparin 30 mg every eight hours (group 2)

Subsequent trough anti-Xa levels will be performed eight hours after the third dose. Repeat anti-Xa levels will be drawn eight hours after the third dose of the new regimen(s) (see attached figures) for patients in the treatment arms and eight hours after the sixth dose for those in the control arm. For patients in group 2, anti-Xa levels will be drawn within 30 minutes of the fourth and eighth doses. If patients continue to be subtherapeutic, the group 1 dose will be increased to 50 mg every 12 hours, while the group 2 dose will remain at 30 mg every eight hours. Group 2 will not have subsequent dose adjustment, as this regimen has not been previously evaluated. Coordinated AT-III and TEG will be performed with the first anti-Xa assessment and the first repeat assessment in the interventional groups. After the initial assessments, weekly anti-Xa and AT-III will be collected on patients requiring dose adjustment for up to 28 days. If the weekly trough anti-Xa level is ≥ 0.3 IU/mL, the enoxaparin dose will be decreased to the previous dose (i.e., enoxaparin 50 mg every 12 hours would be decreased to 40 mg every 12 hours; enoxaparin 40 mg every 12 hours would be decreased to 30 mg every 12 hours; enoxaparin 30 mg every eight hours would be decreased to 30 mg every 12 hours) with patient remaining in enrolled study group for all outcome analyses.

Randomization

Following informed consent, serum AT-III and anti-Xa values will be assayed per protocol. Patients with an anti-Xa level < 0.1 IU/mL undergo unblinded 1:1 randomization to ensure equal allocation to each intervention group. Randomization will be performed by study personnel. If the standard of care anti-Xa per trauma protocol is not collected or inappropriately drawn/mistimed by nursing or phlebotomy staff, patients will be able to have a repeat standard of care anti-Xa within 24 hours of initial draw for assignment to treatment or control groups for enrollment and outcome analysis (protocol amendment). This practice aligns with the current daily trauma protocol operations.

Data Collection:

Coordinated serum anti-Xa, AT-III, and TEG will be collected as previously described. Time to goal anti-Xa achievement will be collected as previously described. Additional data to be collected include patient sex, age, weight, body mass index (BMI), body surface area (BSA), injury mechanism (blunt vs. penetrating), ISS, abbreviated injury score ([AIS] for head, chest, abdomen, extremity, cervical spine, thoracic spine, and lumbar spine), RAP, admission and highest serum creatinine, admission and lowest creatinine clearance (Cockcroft and Gault calculated), admission unit (e.g., ICU; floor), time to enoxaparin initiation, heparin initiation (days and number of doses) prior to enoxaparin therapy, VTE events specified, length of stay (hospital and ICU), 28-day mortality, major and minor bleeding events, overall mortality, interruption of study drug, cumulative fluid balance from admission with each serum assay, total milliliters of transfused fluid to date at each anti-Xa assessment, and milliliters of packed red cells transfused in specified time frame.

Specimen collection

Serum assays will be collected as previous described. In summary, initial AT-III and anti-Xa concentrations will be performed eight hours after the third dose of enoxaparin 30 mg q12h. Repeat anti-Xa assessment will be performed after the third dose of the new enoxaparin regimen, based on patient randomization. Coordinated AT-III and TEG will be performed with the first anti-Xa assessment and the first repeat assessment in the interventional group. After the initial assessments, weekly anti-Xa and AT-III will be collected on patients requiring dose adjustment for up to 28 days. All serum anti-Xa and coordinated AT-III and TEG will be drawn 30 minutes prior to stated dose.

Subjects will have the serum assays drawn by either nursing staff via central catheter access or phlebotomy via peripheral venous access. All labs will be drawn using two 2.7 mL blue top, sodium citrate tubes. One tube is needed for the TEG, while the other is used for the AT-III and anti-Xa.

Potential Benefits

VTE are associated with a high morbidity and mortality. Optimal LMWH dosing has not been established for critically injured patients who have altered pharmacokinetics due to altered volume of distribution and metabolism, variable age and weight, and potential decreases in AT-III. Subtherapeutic serum anti-Xa trough concentration has been associated with increased risk for VTE. This pilot clinical investigation has the potential to revolutionize enoxaparin dosing and VTE prevention through anti-Xa guided dosing. Thorough evaluation of risk factors for reduced anti-Xa may provide a focused assessment of patients requiring anti-Xa assessment and subsequent dose adjustments. Overall, optimal enoxaparin dosing will result in fewer VTE events without increasing bleeding risk with an anti-Xa driven adjustment. Improved patient outcomes, expansion of scientific knowledge, and development of VTE prevention protocols may result.

Potential Risks, Discomforts, and Inconveniences

Level of Risk

VTE risks with inadequate prophylaxis have been previously justified above. Risks of increased enoxaparin doses include major and minor bleeding events. Risks will be mitigated by appropriate exclusion of patients with low body weight and increased serum creatinine / decreased creatinine clearance. Serum assays for risk of bioaccumulation will be performed weekly with subsequent dose reduction. Additionally, patient serum creatinine and creatinine clearance will be assessed daily by the trauma team with appropriate therapy modification should patient's renal function worsen. Patients with a 50% change in serum creatinine or an absolute change in serum creatinine by 1 mg/dL will be removed from the study. If these changes in renal function occur after patient has received initial laboratory assessment (i.e., anti-Xa; AT-III; TEG) will be included in the primary outcome analysis.

Blood volume loss due to serum anti-Xa, TEG, and AT-III assay as described above is minimal (2.7 mL x 2). Patients requiring peripheral vein access for serum assays will be at risk for pain/discomfort, bruising, fainting, and infection from phlebotomy sites.

Data Safety Monitoring Plan

Collected data will be screened for adverse events. [name] will act as medical monitor and review collected data and all adverse events to ensure patient safety.

Data Analysis

Primary Endpoints

1. Initial AT-III activity between the control group and the intervention group.
2. Proportion of patients reaching goal anti-Xa between group 1 and group 2 overall, at first repeat assessment, and at second repeat assessment.
3. Median time to achievement of goal anti-Xa between group 1 and group 2.

Secondary Endpoints

1. Patient outcomes to be compared between control and intervention groups including all VTE events (i.e., pulmonary embolism; upper extremity deep venous thromboembolism [DVT]; proximal lower extremity DVT; distal lower extremity DVT), major bleeding (i.e., hemoglobin decrease of ≥ 2 g/dL in a 24 hour period requiring ≥ 2 units of packed red blood cells while on enoxaparin; worsened or new intracranial hemorrhage while on enoxaparin; repeat surgical intervention due to hemorrhage while on enoxaparin), minor bleeding (minor gastrointestinal bleeding [coffee ground emesis with or without < 2 units packed red cell transfusion needed while on enoxaparin]; interruption of study drug by trauma team; other overt bleeding not characterized a major while on enoxaparin), total transfusion requirements after 48 hours until discharge or admission day 28.
2. Proportion of patients with enoxaparin bioaccumulation (defined as an anti-Xa ≥ 0.3 IU/mL at any assay) between group 1 and 2.
3. Risk factor determination for low anti-Xa.

Statistical analyses will be performed using SAS version 9.3 (SAS Institute, Inc., Cary, NC). An intention-to-treat model will be used for data analysis. Patients excluded due to change in renal function will be included in the primary outcome analysis, but not patient outcome analyses for VTE and bleeding outcomes. Nominal data will be reported using frequencies of occurrence and proportions as appropriate. Continuous data will be reported using means and standard deviations or medians and ranged as appropriate per distribution. Hypothesis testing for nominal data will be performed using the Fisher's exact test or chi square test as required based on sample size. Continuous data will be compared using student's t-test/ANOVA or rank sum/Kruskal-Wallis ANOVA for normally distributed and non-normally distributed data, respectively. A p-value < 0.05 will designate statistical significance. Time-to-event analyses will be compared as appropriate and presented as Kaplan-Meier curves. Multivariate logistic regression will be performed for low anti-Xa risk determination. All values with a p-value < 0.2 will be included in the model. Serum AT-III, weight, and age will be forced into the model, regardless of p-value.

A total of 200 patients will be enrolled. Assuming that 50% of patients will have an undetectable anti-Xa on enoxaparin 30 mg every 12 hours, we hypothesize the intervention group will have an absolute reduction in AT-III activity of 10% compared to the control group if the control group has a mean AT-III activity of 80% with a standard deviation of 25%. Secondly, we hypothesize that there will be an absolute difference of 27% in the proportion of patients who achieve goal anti-Xa between group 1 and group 2, assuming 50% of group 1 achieves goal. To achieve an 80% power with an alpha of 0.05 for both outcomes, goal enrollment is 200 patients (table 2).

Table 2. Power analysis for each outcome

AT-III activity difference between control and intervention			
Absolute difference in means	Standard Deviation		Sample Size
10%	25%		200
10%	30%		286
10%	10%		34
20%	30%		74
20%	10%		12
Anti-Xa ≥ 0.1 IU/mL attainment between group 1 and group 2			
Group 1 Proportion	Group 2 Proportion		Sample Size
50%	77%		100
50%	75%		116
60%	80%		164
80%	90%		398
70%	80%		588
VTE reduction between study groups			
Estimate Source	Control Proportion	Intervention Proportion	Sample Size
Malinoski ¹⁵	37%	11%	98
Droege ¹⁷	14.5%	5.5%	390
2013 UCMC Trauma Registry VTE	5.5%	2.5%	1468
2013 UCMC Trauma Registry VTE	5.5%	4.5%	6576

Data storage and confidentiality (include sample storage if applicable)

A single, central, electronic database will be constructed using Microsoft Excel® for storing all study-related data (attached). The database will be password protected such that only authorized study personnel can access the data. Data will be maintained in a confidential manner with regular reminders of the need for confidentiality provided from the senior investigator. A single subject log will be kept for matching patient study number, initials, medical record number, and admission date (attached). Once assigned to the log, patients will only be evaluated using their de-identified, study number. Data entered into the electronic database will be de-identified.

Once the study has been completed, the electronic database will be maintained in a locked office, per the IRB specifications. Only study personnel will have access to the data. Once the IRB-approved time has elapsed, all materials will be destroyed.

Study Population

Patients admitted to the UCMC trauma service are eligible for enrollment.

Inclusion Criteria

- a. Patients with an anticipated length of stay of at least 72 hours
- b. High-risk patients initiated on enoxaparin 30 mg every 12 hours per the existing VTE prophylaxis protocol
 - a. High-risk is defined as patients with a risk assessment profile (RAP) ≥ 5 .¹⁹
 - b. Trauma team VTE prophylaxis protocol contraindications to chemical prophylaxis include
 - i. Intracranial bleeding (e.g., chemical prophylaxis contraindicated within 24 hours of documented stable head computed tomography [CT]),
 - ii. Incomplete spinal cord injury with hematoma within 24 hours post-injury
 - iii. Ongoing hemorrhage
 - iv. Uncorrected coagulopathy
 - v. \geq grade IV liver or spleen injury
 - vi. Intraocular injuries.
- c. Age 18 – 80 years old

Exclusion Criteria

- a. Renal dysfunction (creatinine clearance < 30 mL/min or patients on continuous renal replacement therapy)
- b. Weight < 50 kg or > 150 kg
- c. Platelet count $< 50 \times 10^3$
- d. Allergy to heparin or low molecular weight heparins
- e. Patients on therapeutic anticoagulation at admission or requiring it within 24 hours of admission
- f. Isolated intracranial hemorrhage
- g. Known hyperbilirubinemia (defined as serum bilirubin > 6.6 mg/dL; interferes with the anti-Xa chromogenic assay)
- h. Patients with a RAP score ≥ 5 without enoxaparin initiated within 72 hours of admission
- i. Pregnancy
- j. Incarceration

Patients with a 50% change in serum creatinine or an absolute change in serum creatinine by 1 mg/dL after randomization will be removed from the study. If these changes in renal function occur after patient has received initial laboratory assessment (i.e., anti-Xa; AT-III; TEG), the patient will be included in the primary outcome analysis per intention-to-treat design.

Consenting process and plan

Patients will be identified as previously described per trauma service. Permission to consent per the trauma team attending will be obtained prior to administration of consent. Patients initiated on enoxaparin 30 mg every twelve hours prior per the trauma protocol who meet inclusion and exclusion criteria will be eligible for consent. Study personnel will administer in the patient's room. Informed consent will be obtained prior to first serum laboratory assay. The trauma team should alert research personnel as soon as possible for administration of informed consent. Patients will be able to be consented and enrolled up to four hours prior to the first serum laboratory assay. At-risk or vulnerable patients unable to give consent will have next of kin consented. Investigators will be available seven days a week and will

continue correspondence with subjects throughout the study and until hospital discharge (see “Informed Consent” form).

Compensation

Patients will not receive any direct compensation for research involvement.

Subject costs

[figure not shown]
There are no additional costs to subjects.

REFERENCES

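### Goal anti-Xa (primary endpoint 3) is observed earlier by schedule in group 2, so a test in elapsed hours can favour group 2 at equal attainment

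*Combined protocol and SAP*

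**What the plan says.** The Primary Endpoints list gives item 3 in one line: "Median time to achievement of goal anti-Xa between group 1 and group 2". The Data Collection section adds "Time to goal anti-Xa achievement will be collected as previously described", but no earlier section states a unit or a starting point for the time. The statistical paragraph of Data Analysis says "Time-to-event analyses will be compared as appropriate and presented as Kaplan-Meier curves". It allows t or rank-sum tests for continuous data and sets significance at p < 0.05.

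Three places set the draw times, and they differ.
- The Intervention section says "Repeat anti-Xa levels will be drawn eight hours after the third dose of the new regimen(s", and then "For patients in group 2, anti-Xa levels will be drawn within 30 minutes of the fourth and eighth doses". For group 1 it adds "If patients continue to be subtherapeutic, the group 1 dose will be increased to 50 mg every 12 hours"; group 2 has no upward step.
- Specimen collection says "All serum anti-Xa and coordinated AT-III and TEG will be drawn 30 minutes prior to stated dose".
- The enrollment flowchart shows a four-hour peak draw and an eight-hour draw after the third dose, then a further draw and weekly draws.

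Some elements of the endpoint can be recovered. The 0.1 IU/mL threshold is in Table 2, and weekly draws run for up to 28 days. The Intervention section calls the repeat levels troughs.

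**The concern.** Goal can be recorded only when blood is drawn. If one group is drawn sooner, its recorded times are shorter even when the same share of patients is at goal at each assessment. If more than half of each group is at goal at the first repeat and draws are on schedule, the two medians are simply the two draw times. A comparison listed as primary could then be significant because of the sampling calendar. The missing unit, origin and rule for patients who leave before goal add to this, because the result depends on them.

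**Working it through.** **Plan's own figure.** Endpoint 3 has no hypothesis and no sample size. The nearest stated figure is 100 patients for attainment of 50% against 77%. With mean proportion 0.635, n per group = [1.96√(2×0.635×0.365) + 0.8416√(0.25 + 0.1771)]² / 0.27² = (1.334 + 0.550)² / 0.0729 = 48.7, so 49 per group and 98 in total. This agrees with the plan to rounding.

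**First repeat trough, hours from the first new dose.**

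| Reading | Group 1 | Group 2 | Gap |
|---|---|---|---|
| Intervention: 8 h after third dose | 2×12 + 8 = 32 | 2×8 + 8 = 24 | 8 |
| Specimen collection, stated dose = fourth | 3×12 − 0.5 = 35.5 | 3×8 − 0.5 = 23.5 | 12 |
| Specimen collection, stated dose = third | 2×12 − 0.5 = 23.5 | 2×8 − 0.5 = 15.5 | 8 |

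**Second repeat.** Assume group 1's raised dose starts at 36 h. Its doses are then at 36, 48 and 60 h, and the draw is at 68 h. Group 2's eighth dose is at 7×8 = 56 h, a gap of 12 h. Drawn 30 minutes before the next dose, the times are 71.5 and 55.5 h, a gap of 16 h.

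**Simulation at equal attainment.** There were 50 patients per group, all randomised, with a two-sided 0.05 test. Each patient has chance p of being at goal at the first repeat and, if not, chance p at the second. Those never at goal are censored at day 28. The plan assumes 50% of group 1 reaches goal without naming the assessment. If that is the total over two draws, 1 − (1 − p)² = 0.5 gives p = 0.293; if it is per draw, p = 0.5. The table gives the percentage of trials significantly favouring group 2 on the 32/68 and 24/56 h clock (2.5% by chance). Repeat runs differ by a point or two.

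| | p = 20% | p = 29% | p = 50% |
|---|---|---|---|
| Log-rank, exact times | 4 | 10 | 44 |
| Log-rank, 6 h SD scatter | 5 | 7 | 19 |
| Log-rank, 12 h SD scatter | 4 | 5 | 11 |
| Log-rank, exact, weekly draws added | – | 6–8 | 37–38 |
| Rank-sum, non-attainers last, exact | 9 | 23 | 79 |
| Rank-sum, non-attainers last, 6 h SD | 7 | 13 | 47 |

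Scored by assessment number instead of hours, the figure is 2.0% to 2.8% each way. The scatter values, and the rule ranking non-attainers last, are assumptions of this check.

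**Hand check of the rank-sum at p = 50%.** Group 2 times are 24 h (0.5), 56 h (0.25) and never (0.25); group 1 times are 32 h (0.5), 68 h (0.25) and never (0.25).
- P(group 2 earlier) = 0.5×1 + 0.25×0.5 = 0.625.
- P(group 1 earlier) = 0.5×0.5 + 0.25×0.25 = 0.3125.
- The expected shift in the rank-sum statistic is (0.625 − 0.3125)×2500/2 = 390.6.
- With expected tie sizes of 25, 25, 12.5, 12.5 and 25, the variance is (2500/12)×(101 − 50681/9900) = 19,975, so the SD is 141.3.
- Expected z = 2.76, and Φ(2.76 − 1.96) ≈ 79%, as simulated.

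**Unit, at p = 50%.** In completed days, 32 and 24 h both fall in day 1, and the rate is 2–3% each way. At 35.5 and 23.5 h they fall in days 1 and 0, and log-rank favours group 2 in about 22%.

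**Group 1's escalation (illustrative second-draw rates, group 1 against group 2).**
- 50% at first repeat, then 50% against 25%: log-rank favours group 2 in 10%; a rank-sum test on assessment number favours group 1 in 9%.
- 50%, then 50% against 0%: log-rank favours group 1 in 9%; assessment number favours group 1 in 22%.
- 29.3%, then 50% against 25%: log-rank favours group 1 in 8.5%; assessment number favours group 1 in 23%.

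**Leaving early.** Inclusion needs only an anticipated stay of 72 h. Group 1's second repeat falls about 36 + 68 = 104 h after the first 30 mg dose, so some patients may leave before it.

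**The case against.** **Earlier confirmation may be real.** Patients dosed every 8 hours may cross 0.1 IU/mL sooner, and the trial compares strategies. That stands as a possibility. Because goal is seen only at draws, an elapsed-time test cannot separate it from earlier sampling.

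**The largest figures need favourable inputs.** They require exact draw times, 50% attainment at each draw in both groups, no weekly draws, or a rank-sum rule that the plan does not state. Log-rank is the closer reading of a plan that specifies Kaplan-Meier curves. This stands: under log-rank the excess is small at low attainment or with wide scatter, and in completed days at exactly 32 and 24 h it is absent.

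**The endpoint is not wholly undefined.** A reader might infer that the four-hour peak could count as goal. The Pharmacokinetic / Safety section says "patients enrolled in the proposed study would achieve a steady state peak between 0.3 – 0.5 IU/mL", so nearly everyone would then qualify by schedule at 28 h (24 + 4) and 20 h (16 + 4). The documents do not support that reading. Low anti-Xa is defined on a trough, the repeat levels are called troughs, and in the flowchart AT-III and TEG accompany the eight-hour draw, not the peak. The phrase about collection as previously described can be taken to mean the draw schedule. Intention-to-treat and the retention of patients removed for renal change also say who is analysed. None of this supplies a unit, an origin or a rule for leaving before goal.

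**It is a pilot, and endpoint 3 is unpowered.** True, but it is listed as primary and falls under the p < 0.05 rule.

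**Conclusion.** The point holds in conditional form. On the readings set out above, group 2's first repeat trough comes 8 to 12 h earlier from the first new dose, and a comparison in elapsed hours can carry that gap into the result when attainment per assessment is equal. Log-rank favours group 2 in about 4% to 44% of trials with exact times, and about 4% to 11% with 12 h scatter, against 2.5% by chance. This rests on 50 per group, two repeat draws, attainment of 20% to 50% per draw and the raised dose starting at 36 h.

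A reader might go further and infer that the trial is bound to declare group 2 faster. The documents do not support that. Attainment and draw-time scatter are unknown, the unit is unstated and can remove the tilt, and group 1's escalation can offset or reverse it. No stated sample size is shown to be wrong. The point should be fixed before analysis because a false primary result is possible and the remedy is cheap.

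**What to change.** 1. Reconcile the draw times in the Intervention section, Specimen collection and the enrollment flowchart, and confirm that only trough draws count as goal.
2. Make the between-group test of endpoint 3 the assessment at which trough goal is first recorded (first repeat, second repeat, weekly, never), in all randomised patients, with an ordinal or discrete-time test. State how patients who are discharged or removed before goal are handled.
3. Report elapsed time descriptively from a stated origin and in a stated unit, noting that it reflects the draw schedule. If elapsed time must be tested, use an interval-censored analysis.
4. If earlier confirmation under dosing every 8 hours is meant to count as part of the strategy, say so in the endpoint.

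The cost is wording of the endpoint and analysis, with no extra samples or patients. The downside is that the tested endpoint overlaps with primary endpoint 2 and is no longer a simple median time.
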